Study Title: An Integrative Technology Approach to Home-based
Conjoint Therapy for PTSD

Study Identifier: NCT02720016

Document Date: 9/28/21

Study Protocol

Research Design and Methods

Study Design Overview: The primary aim of this 4-year RCT is to evaluate the superiority of CBCT delivered via two modalities (i.e., office-based [CBCT-OB] and home-based via CBT [CBCT-HB]) compared to a clinic-based PTSD Family Education (PFE) control condition on clinical efficacy (PTSD symptoms, relationship quality, functional impairment) and process outcomes (Figure 1). Participating couple (N = 137 dyads) at a US Department of Veterans' Affairs (VA)-based clinical site were randomly assigned to one of three treatment arms (CBCT-OB, CBCT-HB, or PFE-OB) and assessed at five time points: pre-treatment, mid-treatment, post-treatment, 3-months post-treatment, and 6-months post-treatment.

The primary analyses are pairwise comparisons of each CBCT modality with the control condition: CBCT-OB vs. PFE control and CBCT-HB vs. PFE control (Stage 1 analyses in Figure 1). These comparisons are considered primary in the sense that establishing superiority of each modality to control is a necessary condition before consideration of each modality's relationship to each other. Progression to Stage 2 testing (comparison of the two CBCT modalities) will occur only if Stage 1 analyses show that both modalities are superior to control; progression to Stage 3 (a non-inferiority trial, not part of the current proposal) occurs only if no statistically significant differences are found for Stage 2.

[figure not shown]
The primary hypothesis predicts that CBCT delivered via either (CBCT-OB and CBCT-HB) modality will result in significantly greater reductions of **PTSD symptoms**,

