Study Title: An Integrative Technology Approach to Home-based
Conjoint Therapy for PTSD

Study Identifier: NCT02720016

Document Date: 9/28/21

Statistical Analysis Plan

Analytic Considerations:

a) Analysis sets. The primary analyses use the ITT sample, which consists of all participants who were randomized. Couples that terminated treatment early were invited to complete follow-up assessments and their data were included in the ITT analyses.

b) Treatment of missing data. Missing data were imputed using multiple imputation procedures in the Blimp software, which uses fully Bayesian model-based specification. In order to explore potential reasons for data missingness, dichotomous treatment status (i.e., non-completion versus completion) was modeled using logistic regression and all subject-level characteristics predicting the retention outcome were included as auxiliary variables in the imputation model.

c) Adjustment for multiple outcomes. To address possible Type I errors due to multiple dependent variables, we specified a priori the primary measures corresponding to the stated a priori hypotheses within the following specified domains: PTSD symptoms, relationship satisfaction and functional impairment. For secondary analyses using additional outcome variables within a given domain, we will report both unadjusted p-values and adjusted p-values using a Tukey-type correction for multiple outcomes. Secondary outcomes and exploratory analyses will be evaluated qualitatively in terms of consistency with primary results and conservatively in terms of statistical significance of results. Sensitivity of study results to adjustment for multiplicity of outcomes will be evaluated.

Preliminary Analyses: All statistical procedures were conducted using SPSS and R software programs. Preliminary analyses examined distributional characteristics of study variables to provide a description of the study sample and to allow for assessment of randomization. Demographic, baseline clinical characteristics of the individual Veteran and/or couple dyad, and other putative prognostic variables (e.g., relationship characteristics) were compared for imbalance across the treatment groups using analysis of variance for continuous variables and chi-square tests for categorical variables. Where, despite randomization, significant group differences at baseline were identified, those variables were included as covariates in sensitivity analyses.

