Model construction. The primary efficacy outcome variables are (1) Veteran-reported PTSD symptom reduction (CAPS severity scores), (2) Veteran- and partner-reported relationship distress (CSI) and (3) Veteran-reported functional impairment (IPF). Secondary variables include PTSD diagnostic status (CAPS), self- reported PTSD symptoms (PCL), depression scores (BDI-II), anger (STAXI-2), and relationship conflict (CTS-2). Variability in scores for each of the primary and secondary outcome measures were examined individually in a series of separate multilevel models. Piecewise/spline models were used to estimate separate slopes for the treatment period and the follow-up period. Each model examined the predictive value of the primary variable of interest: (1) two time slopes (treatment and follow-up; fixed effects), (2) treatment group (fixed effects), and (3) the cross-level interactions of time*treatment group (fixed effects). Baseline scores on the dependent measure were also included as a model covariate, to control for their effect. For couple-based outcomes (e.g., CSI scores), between-dyad, within-dyad, and mixed variables were coded in the model as described by Campbell and Kashy, 2002. As preliminary analyses indicated an imbalance both relationship length and partner-reported CSI scores between treatment groups, subsequent sensitivity models were conducted to control for their effects. For Stage 1 analyses (Aim 1a), pairwise unadjusted and covariate-adjusted differences in least squares means for each outcome variable were compared at mid-treatment, post-treatment, and at the 3- and 6-month follow-up time points using appropriate model

contrasts (i.e., CBCT-OB vs. PFE and CBCT-HB vs. PFE). Next, in Stage 2 analyses (Aim 1b), unadjusted and least squares adjusted means from the GLMM contrast comparisons, along with corresponding 95% CIs, provided estimates of the magnitude (effect sizes), direction, and statistical significance of differences in outcome measures for CBCT-OB compared to CBCT-HB. Progression to a fully powered non-inferiority trial (Stage 3, Figure 1) was determined to occur only if both CBCT delivery modalities are superior to the control intervention (Aim 1a and b). This study provides necessary input information (e.g., variance-covariance and effect size estimates) for the design of the subsequent non-inferiority study.

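### Extra covariates are chosen by baseline significance tests, and the Stage 1 comparison that gates Stage 2 is made both unadjusted and covariate-adjusted without defining 'unadjusted' or naming the deciding version

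*SAP*

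**What the plan says.** **Selection rule.** Under Preliminary Analyses, the SAP says that demographic, clinical and other putatively prognostic baseline variables "were compared for imbalance across the treatment groups using analysis of variance for continuous variables and chi-square tests for categorical variables". Where "significant group differences at baseline were identified, those variables were included as covariates in sensitivity analyses". It gives no significance level and no closed list of candidate variables.

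**What the rule picked.** Under Model construction, the SAP reports an "imbalance both relationship length and partner-reported CSI scores between treatment groups, subsequent sensitivity models were conducted to control for their effects".

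**What is adjusted for regardless.** The same section states: "Baseline scores on the dependent measure were also included as a model covariate, to control for their effect".

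**The Stage 1 comparison.** The sentence after the one on imbalance says that "pairwise unadjusted and covariate-adjusted differences in least squares means for each outcome variable were compared at mid-treatment, post-treatment" and at both follow-up visits. The Stage 2 sentence again refers to unadjusted and adjusted means.

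**What Stage 1 decides.** Protocol, Study Design Overview: "Progression to Stage 2 testing (comparison of the two CBCT modalities) will occur only if Stage 1 analyses show that both modalities are superior to" the PFE arm.

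**Therapist.** Protocol, Randomization Procedures: when several therapists were available, randomisation was run separately for each, with priority to an Oceanside therapist for couples from that area. The SAP (Statistical approach) mentions therapist only as a possible cluster effect to be tested with random effects.

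**The concern.** There are two linked weaknesses.

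1. The selection rule asks the wrong question. In a properly randomised trial, any baseline difference is due to chance, so the test says nothing about whether a variable should be adjusted for. That depends on its relation to the outcome. A strongly prognostic variable with a moderate, non-significant imbalance is left out, while a weak one with a large chance imbalance goes in.

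2. The Stage 1 sentence places two versions of each contrast side by side without saying which one establishes superiority or what happens if they disagree. The labels are also unclear. Every model as described already contains the baseline outcome score, so 'unadjusted' could mean without the two imbalance covariates, or without the baseline score as well. For the CSI outcome the line is blurred further, because baseline CSI is already in the main model.

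Stage 1 is both the primary test and the gate to Stage 2. Without a named deciding version, a reader cannot tell which estimate opens the gate, and the text does not exclude relying on the more favourable one.

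**Working it through.** The documents give no Stage 1 alpha, sidedness, power, SD or correlations, so there is no design figure to reproduce. What follows sizes the effect under stated assumptions.

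**Inputs.**
- From the protocol: 137 couples allocated 1:1:1, so 137/3 = 45.7 per arm.
- Assumed: two-sided alpha of 0.05; one contrast at one time point; a linear model in place of the piecewise GLMM.

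**Step 1: how often the tests pick something by chance.** With *k* independent candidates tested at 5% (assumed), P(at least one) = 1 - 0.95^k.
- k = 10: 1 - 0.95^10 = 0.40
- k = 20: 1 - 0.95^20 = 0.64

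Finding some significant imbalance is therefore unremarkable.

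**Step 2: either version may count, fixed covariate set.** Under the null, the unadjusted and adjusted z statistics correlate at √(1 - R²), where R is the multiple correlation of the added covariates with the outcome. P(either |z| > 1.96) from the bivariate normal:

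| R (assumed) | Correlation of z's | Error rate |
|---|---|---|
| 0.3 | 0.954 | 6.4% |
| 0.4 | 0.917 | 6.9% |
| 0.5 | 0.866 | 7.3% |
| 0.6 | 0.800 | 7.8% |

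**Step 3: simulation.** Three arms of 46, 8,000 runs per setting, Monte Carlo SE about 0.25-0.3 percentage points. Assumed: baseline-outcome correlation 0.5-0.7 for fixed covariates and 0.5 for selected ones; extra covariates explain 5-30% of outcome variance (10-30% for selected ones).

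| Setting | Either version p < 0.05 |
|---|---|
| Two fixed covariates, baseline score in both versions | 6.5-8.6% |
| Two fixed covariates, 'unadjusted' also drops the baseline score | 7.5-9.8% |
| Picked by ANOVA from 10 or 20 candidates, all runs | 5.3-6.1% |
| Same, only runs where something was picked | 5.9-7.4% |

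In the selection settings, the unadjusted model alone gave 4.8-5.3% in the same runs. The second reading added 0.4 to 0.8 percentage points (for example 5.35 - 4.91 = 0.44 and 6.08 - 5.25 = 0.83). Counting only the favourable direction, against a nominal 2.5%, the range over all settings was 2.6-4.9%. A single model named in advance stays near 5% (4.6-5.4% without the extra covariates; 4.4-5.4% with a fixed set).

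**Step 4: what the selection rule misses.** Take a 0.3 SD imbalance between two arms of 45.67.
- t = 0.3 × √(45.67/2) = 1.43, p = 0.155. On a comparison of those two arms it would not be picked.
- If the covariate correlates 0.5 with the outcome and is unrelated to the baseline score, the treatment difference shifts by 0.5 × 0.3 = 0.15 SD.
- If it is related to the baseline score, much of this is already removed. Assume outcome-baseline correlation 0.6, covariate-baseline 0.5 and covariate-outcome 0.5. The partial slope is (0.5 - 0.6 × 0.5)/(1 - 0.5²) = 0.267. The residual imbalance is 0.3 - 0.5 × (0.5 × 0.3) = 0.225. The shift is 0.267 × 0.225 = 0.06 SD.

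**The case against.** The strongest reply is that the plan already ranks its analyses. Preliminary Analyses and Model construction both call the models with test-selected covariates sensitivity models, and the Stage 1 sentence follows directly. Its natural reading is a main model accompanied by those sensitivity models. This stands in part. A reader might infer that the SAP declares two co-primary analyses, or allows superiority to rest on whichever is favourable. The documents say neither. What remains is a missing statement, together with tension between the sensitivity label and a Stage 1 comparison made on both versions.

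Further points on that side:
- **Adjustment is not wholly test-driven.** The baseline outcome score enters every model, and the candidates include variables considered prognostic. This is correct and limits the harm, but it does not justify the test as the rule for choosing among them.
- **'Chosen after seeing the data' can mislead.** A reader might infer that outcomes guided the choice. Nothing shows this: a stated rule was applied to baseline variables.
- **The inflation is small.** Under the plan's own selection rule it is about one percentage point or less overall. Stage 2 also requires both modalities to be superior, so under a global null the gate opens falsely less often than a single contrast does. Both points stand.
- **Therapist is not a simple stratum.** Separate randomisation applied only when several therapists were available, with a geographic priority. This is fair, but it is still a reason to include therapist always rather than leave it to a test.

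**Conclusion.** The concern holds in a limited form. The covariate-selection rule is unsound in principle, and the SAP neither defines 'unadjusted' nor names the version of the Stage 1 contrast that decides superiority.

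The numerical consequence is modest. If either version could count, a nominal 5% contrast becomes about 5.3-6.1% overall under test-based selection, and 5.9-7.4% when something is selected, as happened here. With a fixed covariate set and R of 0.3-0.6 it becomes 6.4-7.8%. It approaches 10% only if 'unadjusted' also drops the baseline score and the covariates are strong. All of these figures rest on an assumed alpha and assumed correlations, and on a single-time-point linear model. Multiplicity over contrasts, visits and outcomes is a separate matter and is not counted.

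A reader might also take 0.15 SD as the bias left by an unselected covariate. That figure needs a covariate unrelated to the baseline score already in the model; under the alternative assumptions above it falls to 0.06 SD.

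The change is worth making because Stage 1 is a gate and should rest on one identifiable model.

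**What to change.** 1. Drop the ANOVA and chi-square baseline comparisons as the rule for choosing covariates. Baseline characteristics can still be described by arm.
2. Name one decisive Stage 1 model per primary outcome: the planned piecewise model with the baseline score of that outcome, plus therapist always included, because randomisation was done within therapist when several were available.
3. Define 'unadjusted', stating whether it omits only relationship length and partner CSI or the baseline score as well.
4. Keep the model that adds relationship length and partner CSI as a labelled post hoc sensitivity analysis that can neither establish superiority nor open Stage 2.
5. Trace the deciding model to an earlier dated record, or disclose that it was set after the imbalances were known. The SAP, dated 9/28/21, is largely in the past tense and already reports them, so rewording alone would not make the choice prespecified.

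**Cost.** A few sentences of SAP text, a check of earlier records, and possibly a refit with therapist in every model. No new data are needed. The downside is fewer versions of the result to quote.

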Participants: To be included in the study, participants must: (1) be a Veteran (age 18 or older) with a current DSM-5 diagnosis of PTSD (as assessed by the CAPS-5) no less than 3 months after the index trauma occurred (to allow for potential natural recovery) and (2) be on a stable psychoactive medication regimen for at least 2 months (if eligible) or (3) be an intimate partner (age 18 or older) who is willing to participate in the intervention. Both members of the couple must be willing to (4) be randomized into any of the three treatment conditions, (5) have assessment and treatment sessions audio recorded; and (6) agree not to receive other individual or conjoint psychotherapy for PTSD during the treatment portion of the study. Finally, consistent with home-based clinical trials and actual clinical practice (7) participants enrolled into the study will need

to have access to internet via DSL or a cable provider in case they are randomized into the home-based condition. If they do not, they will be provided a VA tablet installed with Wi-Fi through the VA clinical TMH program. The frequency of occurrence of no internet service will be tracked.

Exclusion criteria are: (1) current substance dependence in either member of the couple not in remission for at least 3 months, as assessed by the Alcohol Use Disorders Identification Test (AUDIT) and Drug Abuse Screening Test (DAST); (2) any current uncontrolled psychotic disorder in either member of the couple; (3) imminent suicidality or homicidality in either member of the couple; (4) any severe cognitive impairment in either member of the couple; (5) any perpetration of severe physical or sexual relationship aggression in the past year (as assessed by the CTS-2-S, EHITS, and a 5-item IPV assessment). Participants who report experiencing severe physical or sexual relationship aggression will be excluded from the study. The partner reporting interpersonal violence will be referred to local resources for victims of domestic violence and given a brochure containing information regarding these resources. Participants who do not meet study criteria will be offered referrals to alternate services, as well as assistance in contacting the referral sites as needed; or (6) Partner cannot have a probable PTSD diagnosis as indicated by a score of greater than 33 on the PCL-5.

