unable to attend an assessment appointment in person, the assessment(s) were offered over the phone. The mid-treatment assessment (between sessions 4 and 5) consisted of self-report questionnaires that the participants completed prior to their mid-treatment therapy session. Both members of the couple completed a baseline assessment interview designed to gather background information and to screen for psychiatric disorders. The PTSD-positive Veteran completed an additional baseline interview to assess PTSD symptoms and DSM-5 diagnosis via the CAPS-5. Participants were advised that each assessment meeting was approximately 2-3 hours in length. Informed consent for each participant was performed by study staff. All diagnostic assessment procedures were performed by the Independent Evaluator (IE) who is trained to administer the CAPS-5 to fidelity via practice interviews until a minimum interrater reliability rating of 90% is achieved. CAPS-5 fidelity was monitored in an ongoing fashion to prevent drift (see Assessment and Treatment Fidelity Monitoring). Study staff (e.g., IE, research assistants) administered self-report questionnaires to the partner and discussed with the IE about inclusion/exclusion criteria. Study staff alerted the therapist if either member of the couple showed a marked worsening of symptoms (e.g., suicidal ideation) or a score of a 2 or higher on item 9 of the BDI-II at any assessment occasion. To minimize the risk of bias, the IE stayed blinded to participants' study condition throughout the study.

Randomization Procedures: Eligible couples were randomly assigned 1:1:1 to receive CBCT-HB, CBCT-OB, or PFE using a permuted block randomization scheme using an excel file, which required confirmation of eligibility criteria before treatment assignment

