Data reliability checks. Reliability and data reduction issues were addressed using descriptive and inferential statistics. Tests of scale reliability will use the Internal Consistency Method and Cronbach's alpha will be calculated. Cronbach's alpha of 0.80 or greater will be considered evidence of sufficient instrument reliability. As described in Assessment and Treatment Fidelity Monitoring, CAPS reliability will be examined via inter-rater agreement.

Analyses for Efficacy Outcomes (Aim 1):

Statistical approach. Longitudinal trajectories of outcomes from baseline to mid-treatment, post-treatment, 3-month, and 6-month follow-up time points were compared using multivariate, multilevel GLMM, which accommodates a wide range of distributional assumptions, including continuous (e.g., CAPS scores, PCL, CSI, IPF, BDI-II, STAXI), categorical/dichotomous (e.g., diagnostic status, treatment completion), ordinal, and count predictors. For outcomes including both members of dyads (e.g., relationship

[figure not shown]
satisfaction), GLMM allowed for modeling multilevel data, as well as for testing other possible cluster effects due to correlation between participants within therapists through inclusion of random effects in the model.

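### PTSD diagnostic status: with a logit link and nominal visit times, the treatment-period slope and its arm interaction have no finite, determinate estimate; the later arm contrasts survive

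*SAP*

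**What the plan says.** SAP, Model construction: "Secondary variables include PTSD diagnostic status (CAPS), self- reported PTSD symptoms (PCL", followed by depression, anger and relationship conflict. It continues: "Variability in scores for each of the primary and secondary outcome measures were examined individually in a series of separate multilevel models". No exception is made for the binary outcome. On time: "Piecewise/spline models were used to estimate separate slopes for the treatment period and the follow-up period". Each model also has treatment group and "the cross-level interactions of time*treatment group (fixed effects"), and "Baseline scores on the dependent measure were also included as a model covariate, to control for their effect". Stage 1 then asks for pairwise contrasts on each outcome at mid-treatment, post-treatment, 3 and 6 months.

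SAP, Statistical approach: "Longitudinal trajectories of outcomes from baseline to mid-treatment, post-treatment, 3-month, and 6-month follow-up time points were compared", with diagnostic status given as an example of a dichotomous variable. For Aim 1 the SAP states no link function, and it does not say whether time is nominal or actual.

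Protocol, Participants: the Veteran must "be a Veteran (age 18 or older) with a current DSM-5 diagnosis of PTSD (as assessed by the CAPS-5"). Under Assessment Administration, the Veteran "completed an additional baseline interview to assess PTSD symptoms and DSM-5 diagnosis via the CAPS-5". Under Randomization Procedures, eligibility had to be confirmed before the assignment was shown. The mid-treatment assessment is limited to questionnaires that participants fill in themselves, whereas the CAPS-5 is an interview by the Independent Evaluator. Diagnosis is therefore observed at four visits: baseline, post-treatment, 3 months and 6 months.

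**The concern.** A treatment-period slope on the log-odds scale runs from the baseline log-odds to the post-treatment log-odds. Here the baseline proportion is 100% in all three arms by design, so the baseline log-odds is infinite. No diagnosis is recorded between baseline and post-treatment to anchor the line.

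The SAP counts the time slopes and their interactions with group among its variables of interest. For loss of diagnosis, the one listed efficacy outcome that expresses remission, the treatment-period estimates would depend on where the software stops or starts. A very large standard error could be read as no treatment effect. An analyst who noticed would have to devise another model after seeing the data, which a SAP should prevent.

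**Working it through.** The documents give no figure for this outcome, so there is nothing to reproduce. The check is whether the specified terms can be estimated.

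**Inputs from the documents.** 137 couples allocated 1:1:1, and 137/3 = 45.7, so about 46/46/45. Baseline diagnosis is positive for all. CAPS is taken at baseline, post-treatment, 3 and 6 months.

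**Assumed inputs.** Logit link and nominal visit times. Probability of still meeting diagnosis after treatment, before adding a random intercept, in PFE/CBCT-OB/CBCT-HB: scenario A 0.70/0.45/0.45, scenario B 0.80/0.60/0.50. The simulated post-treatment rates were 0.74/0.52/0.44 and 0.74/0.59/0.47.

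**Step 1: algebra.** Let a_g be the baseline log-odds in arm g, b_g the treatment-period slope (time coded 0 at baseline, 1 from post-treatment on), and t_g = a_g + b_g the post-treatment log-odds. In ordinary logistic regression the later visits involve a_g and b_g only through t_g. The baseline rows contribute n_g × log[1/(1 + exp(−a_g))], which rises without limit of a_g. For any t_g, the likelihood is therefore highest as a_g goes to infinity, and b_g = t_g − a_g goes to minus infinity. The interaction is

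b_OB − b_PFE = (t_OB − t_PFE) − (a_OB − a_PFE).

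The first bracket is estimable. The second is a difference of two infinities.

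**Step 2: logistic fits, scenario A.**

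| Iterations | Intercept | Treatment slope | SE of slope | SE of slope × OB |
|---|---|---|---|---|
| 10 | 11.6 | −10.5 | 29 | 41 |
| 20 | 21.6 | −20.5 | 4,310 | 6,095 |
| 25 | 26.6 | −25.5 | 52,508 | 74,257 |

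The last column is √2 times the one before (√2 × 4,310 = 6,095), because two arms of 46 each contribute an undefined baseline. Scenario B gives the same standard errors, with slopes −10.67, −20.67 and −25.67. Its printed interaction stays at −0.57 only because the algorithm pushes both baselines out equally.

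**Step 3: random intercept.** In scenario A, fixing the common intercept at 3, 5, 8, 12, 16 and 20 gives −2 log L of 536.04, 517.65, 513.73, 513.50, 513.498 and 513.498. It falls and then flattens, with no finite optimum. In a separate simulation (46 per arm, random-intercept SD 1.5), three starting values gave interactions of 0.74, 1.36 and 3.30 at the same log-likelihood.

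**Step 4: mid-treatment contrast.** If mid-treatment is coded 0.5, its log-odds is (a_g + t_g)/2. The arm contrast contains (a_OB − a_PFE)/2, so it is undetermined too.

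**Step 5: baseline covariate.** The model has 9 columns: intercept, two slopes, two arm indicators and four interactions. Baseline diagnosis makes 10, but it equals 1 for everyone and copies the intercept: rank 9 of 10. Dropping it changes no other estimate.

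**Step 6: what survives.** In the same fits the follow-up slope has SE 0.08 and its interactions 0.10 to 0.11. The post-treatment OB versus PFE log-odds contrast is −1.07 (SE 0.41) in A and −0.57 (SE 0.40) in B. Fits to the post-treatment, 3- and 6-month rows alone give the same values. These come from ordinary logistic fits that ignore within-Veteran correlation, so they show that the contrast is finite, not what precision to expect.

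**Step 7: dropping the baseline row but keeping the slope.** Treatment time then equals 1 in every row, so the slope copies the intercept and its two interactions copy the arm indicators: 9 − 3 = 6, rank 6 of 9. The divergence goes, but the treatment-period terms are still not estimable.

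**The case against.** A reader might infer that the outcome cannot be analysed at all, or that a remission difference could not be shown. The documents do not support that. Stage 1 rests on arm contrasts at the visits, and those at post-treatment, 3 and 6 months are finite and unaffected. This part of the objection stands in full.

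An all-positive baseline is also not enough by itself. With a hypothetical mid-treatment CAPS the slope was finite (scenario A −2.55, SE 0.79; scenario B −2.82, SE 0.79). The self-report-only mid-treatment assessment is a necessary premise, and the protocol supplies it.

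The failure depends on choices the SAP leaves open. An identity link gives a finite slope, in essence the post-treatment proportion minus 1. Actual visit times can do so as well: with assumed treatment-period times of mean 12 weeks and SD 2 or 4, simulated fits converged, with slopes from −0.85 to −3.11 (SE 0.37 to 0.82) and OB interaction SEs of 0.51 to 1.09. This stands as a condition on the conclusion. Such a model may fit poorly, since its slope rests on a straight line in log-odds and on the spread of visit dates.

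The constant covariate is harmless, and the baseline score could be read as CAPS severity. That reading rescues the covariate but not the slope.

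Finally, dropping the baseline row to avoid using baseline twice would remove the divergence. It would not restore the slope, which becomes aliased with the intercept. That aliasing comes from the CAPS schedule and is not special to the binary outcome.

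**Conclusion.** The concern holds in a limited form. For diagnostic status, under the stated model with a logit link and nominal visit times, the treatment-period slope and its arm interaction have no finite, determinate estimate, and the mid-treatment contrast is not identified. For those terms the loss is complete, whatever the true effect. For the follow-up slope, its interaction and the post-treatment, 3- and 6-month contrasts it is nil. The algebra does not depend on the assumed remission rates; the simulated figures only illustrate it.

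Primary CAPS severity varies at baseline, so this separation does not touch it. Severity is low: one secondary outcome is affected, and the SAP already plans to read secondary outcomes qualitatively and conservatively.

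**What to change.** Add one sentence to Model construction, for PTSD diagnostic status only. Model the post-treatment, 3- and 6-month responses with a logit link and terms for arm, visit and arm by visit. Use baseline CAPS-5 severity as the covariate in place of baseline diagnosis. Omit the baseline row, the treatment-period slope and the mid-treatment contrast. Report arm differences in the proportion no longer meeting diagnosis at each visit.

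The cost is a re-run of one secondary model, with no new data. If the imputations for this outcome were generated from the slope model, which the SAP does not say, they should be regenerated to match. The outcome loses its treatment-period slope, which the current model does not deliver under a logit link with nominal times.
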